3.2.2. Safety Population

The Safety Population is defined as all patients who receive at least 1 dose of investigational combination treatment regimen, will be used in the safety analyses, regardless of the duration of treatment. The data will be presented by groups and overall. The Safety Population will be used for safety analyses as well as for demographics, and baseline characteristics.

3.3. Disposition

The number and percentage of patients in the efficacy evaluable population, patients in the safety population, patients who completed the study, and patients who were prematurely terminated from the study will be summarized.

According to study protocol Section 7.3, a patient may be discontinued from the study at any time if the patient or Investigatory determines that it is not in the best interest of the patient to continue participation.

For patients who discontinued from the study, the reasons for discontinuation will be summarized for the following categories:

- Adverse event
- Disease progression
- Loss to follow-up
- Withdrawal of consent
- Non-Compliance with study drug
- Physician Decision
- Pregnancy
- Protocol deviation
- Study terminated by sponsor
- Other

Patients' completion/discontinuation status will be listed, including patient identifier, informed consent date, date of completion/discontinuation and, for those who discontinued early, the specific reason(s) for discontinuation.

3.4. Protocol Deviations

Major protocol deviations will be summarized and listed by each category. All protocol deviations identified according to study entry criteria and during treatment will be listed.

3.5. Demographics and Baseline Characteristics

Demographics and baseline characteristics will be summarized for the Safety Population. Age (years), height (cm), weight (kg), and BMI (kg/m²) at baseline will be summarized descriptively. Sex, race, ethnicity, BMI category (underweight: <18.5 kg/m²; normal: 18.5 to <25 kg/m²; overweight: 25 to <30 kg/m²; obese: \geq 30 kg/m²), and ECOG performance status (0, 1, 2, 3, 4, or 5) will be summarized by frequency counts. Body mass index is calculated based on weight and height at baseline.

Demographic data and baseline characteristics (as detailed above) as well as informed consent date will be provided in listings.

3.6. Cancer Disease History

Cancer disease history will be summarized. The number and percentage of patients in each of the following categories will be presented.

- Method of Initial Diagnosis
- Primary Origin of Tumor Type

The time from initial diagnosis to first dose (years) and time from most recent disease progression to first dose (weeks) will be summarized descriptively.

Cancer disease history will be listed for the Safety Population.

3.7. Medical History

Reported medical history terms will be coded using Medical Dictionary for Regulatory Activities (MedDRA) version 21.0 or higher. General medical history information will be summarized by category of medical history being collected. Medical history will be listed for the Safety Population.

3.8. Prior Cancer Related Therapies

A frequency tabulation of the number of patients with previous cancer-related surgery, radiation therapy, and systemic therapy including line of therapy will be provided. In addition, tabulation will be provided by location of radiation therapy and type of previous systemic therapy.

3.9. Prior and Concomitant Medications

A prior medication is defined as any medication taken with an end date prior to the first dose of study drug. A prior regimen can contain more than one prior medications. A concomitant medication is defined as any medication (1) that started before the first dose of study drug and was continuing at the time of the first dose of study drug, or (2) started on or after the date of the first dose of study drug and continued up to 30 days after the patient's last dose of study drug.

The number and percentage of patients who have taken prior or concomitant medications will be summarized using the WHO-ATC generic drug name dictionary (version: March 2016 or higher) for the Safety population.

For the summary table, if a subject has taken a concomitant medication more than once, the subject will be counted only once for that medication. A patient who reports the use of two or more medications with same start date will be counted only once in the summary of "Any Concomitant Medication." Similar rules will apply to prior medications as well.

The concomitant medication will be reviewed by medical team to identify the anti-cancer therapy treatment during the study.

All reported medications (including prior medications and concomitant medication) will be included in listing.

3.10. Extent of Exposure

For each study drug, the ALKS 4230 and the pembrolizumab administration profile will be summarized with respect to treatment duration, total number of ALKS 4230 and pembrolizumab infusions, cumulative dose (μ g/kg) of ALKS 4230 and pembrolizumab (mg) administered, and number of cycles.

The following items will be summarized for both ALKS 4230 and pembrolizumab:

Duration of Exposure (Days) = min (Last date of exposure, death) – Date of first dose

Last date of exposure = Initial dose date of the last cycle +21 - 1

Duration of Treatment (Days) = Date of last dose – Date of first dose + 1

Number of Cycles received (Cycles) = Number of cycles with at least one study drug

Total Dose Received during a Cycle= Sum of Doses received during that cycle

Cumulative Dose = Sum of (Total Dose Administreated during a Cycle)

Number of patients with dose reductions, dose interruptions will be summarized by counts and percentages.

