9.5.3. Dose Modifications

Dose reductions of pembrolizumab are not permitted on study. Refer to Section 9.5.1 for guidelines on dose delays.

The decision to continue pembrolizumab or to remove the patient from protocol therapy will be made at the discretion of the Investigator and/or the Sponsor and the SRC.

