#### 9.5.4.2. Events Considered Related to Pembrolizumab

Adverse events associated with pembrolizumab exposure may represent an immunologic etiology. These AEs may occur shortly after the first dose or several months after the last dose of treatment. Pembrolizumab must be withheld for drug-related toxicities and severe or life-threatening AEs. Refer to the Keytruda USPI for dose management of toxicities related to pembrolizumab.

Pembrolizumab may be interrupted for situations other than treatment-related AEs, such as medical/surgical events or logistical reasons not related to study therapy. Patients should be placed back on study therapy within 3 weeks of the scheduled interruption unless otherwise discussed with the Sponsor. The reason for interruption should be documented in the patient's study record.

Pembrolizumab will be

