## **12.3.** Relationship to Study Drug

The assessment of the relationship of study drug to each AE will be reported on the appropriate source document (and SAE form, in the event of an SAE) by the Investigator (or designated sub-Investigator) according to his or her best clinical judgment. The criteria listed in Table 13 should be used to guide this assessment. Please note that not all criteria must be present to be indicative of a particular drug relationship. All study drugs are considered "test drugs" for the purposes of the definitions listed in the table.

Relationship	Criteria for assessment
Definitely related	There is evidence of exposure to the test drug
	AND
	The temporal sequence of the AE onset relative to administration of the test drug is reasonable
	The AE is more likely explained by the test drug than by another cause.
	Dechallenge (if performed) is positive
	Rechallenge (if feasible) is positive
	The AE shows a pattern consistent with previous knowledge of the test drug or test drug class
Probably related	There is evidence of exposure to the test drug
	AND
	The temporal sequence of the AE onset relative to administration of the test drug is reasonable
	The AE is more likely explained by the test drug than by another cause
	Dechallenge (if performed) is positive
Possibly related	There is evidence of exposure to the test drug
	AND
	The temporal sequence of the AE onset relative to administration of the test drug is reasonable
	The AE could have been due to another equally likely cause
	Dechallenge (if performed) is positive
Probably not	There is evidence of exposure to the test drug
related	AND
	There is another more likely cause of the AE
	Dechallenge (if performed) is negative or ambiguous
	Rechallenge (if performed) is negative or ambiguous
Definitely not	The patient did not receive the test drug
related	OR
	Temporal sequence of the AE onset relative to administration of the test drug is not reasonable
	OR
	There is another obvious cause of the AE

Abbreviation: AE=adverse event.

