- Any TEAE with NCI CTCAE toxicity ≥Grade 3 and related to ALKS 4230 as assessed by the Investigator
- Any TEAE with NCI CTCAE toxicity ≥Grade 3 and related to pembrolizumab as assessed by the Investigator
- Any Treatment Emergent Serious Adverse Event (SAE)
- Any SAE related to ALKS 4230 as assessed by the Investigator
- Any SAE related to pembrolizumab as assessed by the Investigator
- Any SAE related to ALKS 4230 with NCI CTCAE
 Grade 3 as assessed by the Investigator
- Any SAE related to pembrolizumab with NCI CTCAE > Grade 3 as assessed by the Investigator
- Any TEAE leading to discontinuation of ALKS 4230
- Any TEAE leading to dose interruption of ALKS 4230
- Any TEAE leading to dose reduction of ALKS 4230
- Any TEAE leading to discontinuation of pembrolizumab
- Any TEAE leading to death

The tables will be sorted by overall descending frequency of SOC and then, within a SOC, by overall descending frequency of PT based on the patient count for the overall column.

The original date and time will be shown on all listings of AEs. Listings will be provided for all TEAEs, serious TEAEs, and TEAEs leading to study treatment discontinuation. The data listings will be provided for dose reductions, and dose interruptions along with the AE/SAE that was associated with the change in dosing for ALKS 4230 and pembrolizumab separately.

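### SAP 3.10 reports cycles received for each drug but counts a cycle if either drug was given, so the count can be too high for a drug that was stopped or skipped

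*SAP*

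**What the plan says.** SAP 3.10 (Extent of Exposure) sets the reporting level by drug: "For each study drug, the ALKS 4230 and the pembrolizumab administration profile will be summarized with respect to treatment duration". The same sentence goes on to infusions, cumulative dose and number of cycles. The definitions are then introduced by "The following items will be summarized for both ALKS 4230 and pembrolizumab", and among them is "Number of Cycles received (Cycles) = Number of cycles with at least one study drug". No drug-specific cycle count is defined anywhere in the SAP. Both agents are study drugs: Protocol 10.1 lists them under that heading.

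Two further items in SAP 3.10 bear on the point. The exposure end date is "Last date of exposure = Initial dose date of the last cycle +21 - 1", which does not say whose last cycle is meant. Duration of exposure runs from the first dose to the earlier of that date and death, again with no drug named.

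**The concern.** A cycle count that is meant to describe one drug is triggered by either. If a patient receives pembrolizumab alone in a later cycle, that cycle is added to the ALKS 4230 count. If a patient receives ALKS 4230 without pembrolizumab, the pembrolizumab count is inflated instead. The row therefore cannot show any difference between the drugs, which is what a by-drug summary is for.

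Safety and tolerability of the combination is a secondary objective (SAP 1.1.2), and exposure to the investigational drug is background for reading the adverse event tables. A wrong count would also disagree with the cumulative dose in the same summary.

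**Working it through.** The documents state no figure that depends on this definition, so there is none to reproduce. The check has two parts: whether the drugs can separate, and what the formula then returns.

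**Can the drugs separate?**

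Text that leaves it possible:
- Protocol 8.3.5 rules out further ALKS 4230 after a Grade 3 or 4 infusion reaction and does not say there that pembrolizumab stops.
- Protocol 9.5.3: "The decision to continue pembrolizumab or to remove the patient from protocol therapy will be made at the discretion of the Investigator". That sentence also names the sponsor and the safety review committee.
- SAP 3.13.2 has a row for "Any TEAE leading to discontinuation of ALKS 4230" and a separate one for discontinuation of pembrolizumab.

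Text that mostly keeps them together:
- Protocol 8.1 (repeated in SAP 1.2): after a toxicity attributed to ALKS 4230 both drugs are held, and the patient may then resume both or leave the study.
- Protocol 9.5.2: a patient who permanently stops study therapy leaves the study.
- Protocol 12.3.1: for immune-related events it is the combination that is withheld or discontinued.

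Protocol 9.5.4.2 says "Pembrolizumab may be interrupted for situations other than treatment-related AEs". It does not say that ALKS 4230 continues meanwhile. If it did, the pembrolizumab count would be the one inflated.

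Parts of Protocol 9.5 are not visible in the public text. One-drug cycles are therefore possible, at an unknown frequency.

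**What the formula returns**

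Inputs: ALKS 4230 at 3 µg/kg on 5 days of each 3-week cycle (Protocol 5.3.2), so 5 × 3 = 15 µg/kg per cycle; 17 pembrolizumab cycles (Protocol 9.1.2) and 5 cycles (the minimum in the synopsis, Duration of Study) as two ends of a range. Assumptions: ALKS 4230 is given at full dose in the first k cycles only, pembrolizumab in all P cycles, with no delays, and the patient is alive at the end.

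- Literal ALKS 4230 count = P; drug-specific count = k; overcount = P − k.
- Cumulative ALKS 4230 = 15k µg/kg; apparent dose per reported cycle = 15k / P.
- Duration of exposure = (number of the last cycle − 1) × 21 + 20 days. The last cycle is P if either drug counts and k if only ALKS 4230 counts.

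| P | k | Literal count | Overcount | Cumulative µg/kg | µg/kg per reported cycle | Exposure days, either drug | Exposure days, ALKS 4230 only |
|---|---|---|---|---|---|---|---|
| 17 | 1 | 17 | 16 | 15 | 0.88 | 356 | 20 |
| 17 | 2 | 17 | 15 | 30 | 1.76 | 356 | 41 |
| 17 | 4 | 17 | 13 | 60 | 3.53 | 356 | 83 |
| 17 | 17 | 17 | 0 | 255 | 15 | 356 | 356 |
| 5 | 1 | 5 | 4 | 15 | 3 | 104 | 20 |
| 5 | 2 | 5 | 3 | 30 | 6 | 104 | 41 |
| 5 | 4 | 5 | 1 | 60 | 12 | 104 | 83 |
| 5 | 5 | 5 | 0 | 75 | 15 | 104 | 104 |

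For example, with P = 17 and k = 2, the overcount is 17 − 2 = 15, the apparent dose is 30 / 17 = 1.76 µg/kg per cycle, and the exposure durations are 16 × 21 + 20 = 356 and 1 × 21 + 20 = 41 days. When k = P the two rules agree.

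**The case against.** The strongest reply is that the line is a slip. The formulas in SAP 3.10 form a generic template: none names a drug, yet the dose sums must be applied drug by drug, since ALKS 4230 is in µg/kg and pembrolizumab in mg. Read in the same way, the cycle line means at least one dose of the study drug being summarised, and nothing is overcounted. The dataset specifications, programming specifications and mock tables are separate documents (SAP 6, 8 and 9) and may already settle it. This is a plausible account of the intention. But it is not what the line says, and a definition with two readings, one of them wrong, should be settled before programming.

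The second reply is that the protocol's general rule after ALKS 4230 toxicity names resuming both drugs or leaving the study, not pembrolizumab alone. The separate discontinuation rows in SAP 3.13.2 classify events by the action taken and do not show that anyone stays on the other drug. This stands as a limit on how often the problem can arise. It does not exclude it, given Protocol 8.3.5 and 9.5.3.

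A reader might go further and infer that the SAP will overstate the tolerability of ALKS 4230, perhaps 8.5-fold (17 / 2). The documents do not support that. The ratio comes from one assumed patient at the extreme of the range. Nothing in either document makes the cycle count the main exposure measure. The same summary gives infusions and cumulative dose for each drug, and SAP 3.13.2 tabulates discontinuation, interruption and reduction of ALKS 4230, so a wrong cycle count would be visible. The error is not one-directional either, because it inflates whichever drug was missed.

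**Conclusion.** The point holds as a defect of definition. Taken literally, SAP 3.10 gives both drugs the same cycle count and overstates it for any drug not given in a cycle in which the other was given. The last-cycle wording could carry the same error into the duration of exposure.

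Per affected patient, the overcount is 13 to 16 cycles in the 17-cycle illustration and 1 to 4 in the 5-cycle illustration. These figures rest on an assumed stopping cycle. The number of affected patients cannot be estimated from the documents and may be zero. The consequence is limited to a descriptive exposure table: no efficacy endpoint, test or confidence interval uses the count. This is a minor correction, and no conclusion about biased tolerability follows from it.

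**What to change.** In SAP 3.10, replace the cycle definition with: *Number of cycles received of ALKS 4230 (pembrolizumab) = number of cycles with at least one dose of that drug.* Add one sentence stating that the first dose, last dose and last cycle in the exposure formulas are those of the drug being summarised. If a regimen-level count is also wanted, keep the either-drug count as its own row and label it as such.

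This definition works whether or not pembrolizumab-only cycles occur, so it takes no position on treatment. The cost is a few lines of SAP wording and the matching programming, with no new data. A row giving ALKS 4230 dose received as a percentage of the planned 15 µg/kg per cycle could be produced from the same data, but it is optional and not part of the correction.

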3.11. Efficacy Analyses

3.11.1. General Considerations

All statistical analyses will be performed at the 5% significance level. All confidence intervals will be 2-sided 95% confidence intervals. Efficacy analyses will be carried out using the Efficacy Evaluable Population. Response to treatment will be evaluated using RECIST v1.1.

Summary statistics (n, mean, standard deviation, median, minimum and maximum for continuous variables, and number [%] of patients in each category for categorical variables) will be provided for all variables. Time-to-event variables will be summarized by Kaplan-Meier plots, medians, and ranges. Data from all study centers will be combined for analysis. No adjustments for multiple comparisons will be applied.

3.11.2. Efficacy Analysis for the Primary Efficacy Endpoint

The primary efficacy endpoint is the rate of new or improved antitumor response (hereafter referred to as objective improvement) after the addition of ALKS 4230 treatment in patients receiving ongoing anti-PD-1 therapy but who have not achieved a CR.

An objective improvement for patients within Group 1 (Cohorts 1 and 2) is defined as:

- SD at screening that improves to PR or CR,
- PR at screening that improves to CR

An objective improvement for patients within Group 2 (Cohorts 3 and 4) is defined as:

• PD at screening that improves to PR or CR

Primary efficacy analysis will be evaluated in patients in the Efficacy Evaluable population for each group separately and overall. The objective improvement rate after continued anti-PD-1 therapy with ALKS 4230 will be summarized by group (Group 1 and Group 2) separately and overall with descriptive statistics.

Objective improvement rate for Group $1 = \frac{\text{number of patients who achieved CR or PR}}{\text{number of patients in Group 1}}$

Objective improvement rate for Group $2 = \frac{\text{number of patients who achieved CR or PR}}{\text{number of patients in Group 2}}$

The analysis of objective improvement rate using an exact binomial test will be conducted separately for each group. The two-sided 95% confidence interval (CI) on objective improvement rate will be estimated by Clopper-Pearson method.

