#### 8.3.10.5. Evaluation of Best Overall Response

The best overall response is the best response recorded from the start of the treatment until disease progression/recurrence (taking as reference for PD the smallest measurements recorded since the treatment started). The patient's best response assignment will depend on the achievement of both measurement and confirmation criteria. Best overall response is described in Table 8 for patients with measurable disease and in Table 9 for patients with non-measurable disease.

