## Table 8:Best Overall Response for Patients with Measurable Disease (ie, Target
Disease)

Target	Non-Target Lesions	New	Overall	Best Overall Response when
Lesions		Lesions	Response	Confirmation is Required
CR	CR	No	CR	≥4 weeks confirmation a
CR	Non-CR/Non-PD	No	PR	$\geq$ 4 weeks confirmation a
CR	Not evaluated	No	PR	
PR	Non-CR/Non-PD/not evaluated	No	PR	
SD	Non-CR/Non-PD/not evaluated	No	SD	Documented at least once $\geq 4$ weeks
				from baseline
PD	Any	Yes or	PD	no prior SD, PR, or CR
		No		
Any	$PD^{b}$	Yes or	PD	
		No		
Any	Any	Yes	PD	

Abbreviations: CR=complete remission; SD=stable disease; PD=progressive disease; PR=partial response; RECIST=Response Evaluation Criteria in Solid Tumors.

- a Only for non-randomized studies with response as primary endpoint.
- b In exceptional circumstances, unequivocal progression in non-target lesions may be accepted as disease progression.
- Note: Patients with a global deterioration of health status requiring discontinuation of treatment without objective evidence of disease progression at that time should be reported as "symptomatic deterioration." Every effort should be made to document the objective progression even after discontinuation of treatment.

See RECIST v1.1 manuscript for further details on what is evidence of a new lesion.

NOTE: For purposes of this trial, confirmation of response will occur at 6 weeks after the response-defining measurements rather than the 4-week point specified in the RECIST v1.1 criteria.

Table 9:	Best Overall Response for Patients with Non-Measurable Disease (ie,
	Non-Target Disease)

Non-Target Lesions	New Lesions	Overall Response
CR	No	CR
Non-CR/non-PD	No	Non-CR/non-PD a
Not all evaluated	No	not evaluated
Unequivocal PD	Yes or No	PD
Any	Yes	PD

Abbreviations: CR=complete remission; PD=progressive disease; SD=stable disease

a 'Non-CR/non-PD' is preferred over 'stable disease' for non-target disease since SD is increasingly used as an endpoint for assessment of efficacy in some trials so to assign this category when no lesions can be measured is not advised

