1.3. Study Endpoints

1.3.1. Primary Efficacy Endpoint

The primary objective of this study is to estimate the response rate to ALKS 4230 in combination with pembrolizumab in patients with HNSCC who have previously received anti-PD-(L)1 therapy but who have not achieved a CR. The primary objective will be assessed for the following 2 groups:

- Group 1: Patients with SD, defined as ≥12 weeks of SD per RECIST v1.1 criteria, or patients with PR with no further reduction in tumor size or response (ie, PR and not improving further) for ≥8 weeks on prior anti-PD-(L)1 therapy
- Group 2: Patients with PD with no prior response to anti-PD-(L)1 therapy after ≥8 weeks on anti-PD-1 therapy or patients currently with PD after prior achievement of a best response of SD or PR and after ≥8 weeks on anti-PD-(L)1 therapy.

The primary efficacy endpoint is the rate of new or improved antitumor response (hereafter referred to as objective improvement) after the addition of ALKS 4230 treatment in patients receiving ongoing anti-PD-1 therapy but who have not achieved a CR. Antitumor activity will be measured by radiological assessment compared to screening. Antitumor response rate of subsets of patients will be based on disease status (defined by PR, SD, or PD based on RECIST v1.1, determined by tumor imaging scans) at screening.

[figure not shown]
An objective improvement for patients within Group 1 (Cohorts 1 and 2) is defined as:

- SD at screening that improves to PR or CR
- PR at screening that improves to CR

An objective improvement for patients within Group 2 (Cohorts 3 and 4) is defined as:

• PD at screening that improves to PR or CR

Baseline scans must be completed within 28 days before the start of treatment. Scans are to be completed according to the time points indicated in the Schedule of Assessments (Table 4 in the protocol). Patients whose response converts from PD or SD to PR or from PR to CR will have a confirmatory scan for tumor assessments 6 weeks after the response-defining scan. Thereafter, timing of tumor assessments will depend on whether or not the patient continues with study drugs.

Patients may receive study drug while waiting for confirmation of PD if they are clinically stable as defined by the following criteria:

- Absence of signs and symptoms (including worsening of laboratory values) indicating disease progression
- No decline in ECOG Performance Status
- Absence of rapid progression of disease

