3.11.3. Efficacy Analysis for the Secondary Efficacy Endpoints

Secondary efficacy endpoints in this study include:

- DOR, PFS, TTP, rate of non-progression at 6 months, and OS
- Antitumor response rate of subsets of patients based on disease status (PR, SD, or PD) at screening
- Antitumor activity as measured by radiological assessment compared to screening

The efficacy analysis for the secondary endpoints will be performed for the following endpoints.

• Duration of Response:

Duration of response (DOR) is defined as the time from the first documentation of response CR or PR (whichever is first recorded) to the first documentation of objective tumor progression or death due to any cause. Patients who are alive and progression free on the analysis cut-off date will be censored at their last evaluable tumor response assessment before initiation of any new anticancer treatment.

Patients with 2 or more consecutive missing response assessments prior to death or a visit with documented progression will be censored at the last date of tumor assessment when the patient was documented to be progression free. The detailed censoring rules for DOR is in section 6.2.3.

DOR will be calculated as follows (in weeks):

(date of disease progression/death – date of first response (CR or PR) + 1)/7

The distribution of DOR will be estimated using Kaplan-Meier methodology. The median point estimate DOR will be provided along with the two-sided 95% CIs based on the Efficacy Evaluable population. Kaplan-Meier curves will be provided.

• Progression-Free Survival:

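### The SAP's primary response count is not tied to the 6-week confirmatory scan, so unconfirmed responses can enter the primary rate

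*SAP*

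**What the plan says.** **Primary definition and formula.** SAP 3.11.2 defines objective improvement in Group 1 as "SD at screening that improves to PR or CR", or PR improving to CR. In Group 2 it is "PD at screening that improves to PR or CR". The rate for each group has as its numerator the "number of patients who achieved CR or PR". Confirmation appears in neither the definition nor the formula. Protocol 11.1 carries the same definition.

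**Best response.** Protocol 8.3.10.5 states: "The patient's best response assignment will depend on the achievement of both measurement and confirmation criteria". Table 8 has a column for the confirmation requirement. Its footnote a limits that requirement to non-randomized studies whose primary endpoint is response, which describes this trial. The note below the table adds: "For purposes of this trial, confirmation of response will occur at 6 weeks after the response-defining measurements rather than the 4-week point".

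**Scan schedule.** SAP 1.3.1 and protocol 8.3.10 and 11.1 provide, for exactly the conversions that make up the primary endpoint, a "confirmatory scan for tumor assessments 6 weeks after the response-defining scan". None of them says what happens to the count if that scan fails to confirm or is missing.

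**Declared changes.** SAP 5 states that the statistical methods are unchanged. SAP 5.1 lists only the efficacy evaluable population.

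**The concern.** The trial is open-label and single-arm, and its primary result is a proportion of responders. A second scan protects that proportion against measurement error around the 30% threshold and against shrinkage that does not last. The protocol builds in this protection and schedules the scan, but the section that computes the rate does not use it. Two programmers could derive different primary rates from the same data, one counting first responses and the other confirmed responses, and each could cite the documents.

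The same uncertainty reaches duration of response. If unconfirmed responders enter that analysis, they add very short durations.

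**Working it through.** **1. The rules side by side**

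| Place | Is confirmation needed to count? |
|---|---|
| SAP 3.11.2, definition and formula | Not mentioned |
| Protocol 11.1, definition | Not mentioned |
| SAP 1.3.1; protocol 8.3.10 and 11.1 | Scan scheduled at 6 weeks, with no consequence stated |
| SAP 3.11.1 | RECIST v1.1 named, with no statement on confirmation of response |
| Protocol 8.3.10.5 | Yes, measurement and confirmation |
| Protocol Table 8, note | Yes, at 6 weeks |
| Protocol Table 8, cells | At least 4 weeks in two rows; no visible entry in the ordinary PR row |
| SAP 3.11.3, TTP | The word confirmed is used, but for progression |

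The mismatch therefore starts inside the protocol (11.1 against 8.3.10.5), and SAP 3.11.2 carries it forward.

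**2. A patient on whom the rules differ.** Assume a baseline sum of 100 mm and 69 mm at the first on-study scan (−31%). This meets the PR threshold of 70 mm (30% decrease). By the target-lesion criteria in protocol 8.3.10.4, PD needs a 20% rise from the smallest sum, 69 × 1.20 = 82.8 mm, and at least 5 mm (82.8 − 69 = 13.8 mm, so that is met). If the confirmatory scan gives a sum above 70 and below 82.8 mm, with no new lesions, the patient no longer meets PR and has not progressed. SAP 3.11.2 read literally counts this patient, while protocol 8.3.10.5 does not.

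A patient with no confirmatory scan raises the same question. SAP 3.2.1 needs only one post-baseline scan for the evaluable population, so a single scan showing PR puts the patient in the denominator and, read literally, in the numerator.

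**3. Direction.** Confirmed responders are a subset of first responders and the denominator is the same. The unconfirmed rate is therefore equal to or above the confirmed rate.

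**4. Size, illustration only.** No sample size, null rate or power is visible, so there is no design figure to reproduce. Group sizes and unconfirmed shares below are assumptions. The interval is the SAP's two-sided 95% Clopper-Pearson interval: lower limit = 0.025 quantile of Beta(x, n − x + 1); upper limit = 0.975 quantile of Beta(x + 1, n − x).

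As a check of the method, the benchmark in SAP 2 is 18% (13% to 24%) in 192 patients. Taking 34/192 gives 17.7% (12.6 to 23.9), and 35/192 gives 18.2% (13.0 to 24.4). Both round to the quoted figures.

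| Assumed n | All first responses | Confirmed only |
|---|---|---|
| 20 | 5/20 = 25.0% (8.7 to 49.1) | 4/20 = 20.0% (5.7 to 43.7) |
| 20 | 5/20 = 25.0% (8.7 to 49.1) | 3/20 = 15.0% (3.2 to 37.9) |
| 30 | 9/30 = 30.0% (14.7 to 49.4) | 6/30 = 20.0% (7.7 to 38.6) |
| 40 | 12/40 = 30.0% (16.6 to 46.5) | 8/40 = 20.0% (9.1 to 35.6) |

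Each unconfirmed response adds 1/20 = 5.0 points, 1/30 = 3.3 points or 1/40 = 2.5 points.

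**The case against.** The strongest reply is that the SAP is silent, not contrary. It evaluates response by RECIST v1.1, repeats the confirmatory scan in its own endpoint section, declares no change of method, and leaves dataset and programming specifications to separate documents. PR and CR in 3.11.2 could then mean responses assigned under protocol 8.3.10.5. This stands in part. A reader might infer that the SAP deliberately drops confirmation, and the documents do not support that, because no sentence admits unconfirmed responses. But no sentence excludes them either. Naming RECIST v1.1 does not supply the rule, since the protocol replaces the interval it attributes to RECIST with its own.

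A reader might also infer that duration of response starts on the wrong date. It does not: SAP 3.11.3 starts it at the first recorded CR or PR, and so does protocol 8.3.10.6. The open question is only which patients enter that analysis.

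Three further points are fair.
- Table 8 is not clean. The 4-week cells disagree with the 6-week note, and the blank PR row may be a merged cell lost in conversion. The requirement rests mainly on the sentence in 8.3.10.5 and the note.
- The protocol assigns local reading to eligibility and patient management, and makes copying images for central review a consent option. It does not say which reading feeds the endpoint, so it cannot be claimed that only local reads will be used.
- The primary objective is estimation, and the illustrated intervals overlap widely.

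**Conclusion.** The point holds as a gap in the definition of the primary numerator, in both SAP 3.11.2 and protocol 11.1. Read literally, the formula can count conversions that protocol 8.3.10.5 would not accept, and this can only hold or raise the rate. The departure is not declared.

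The documents do not show that the reported rate will be inflated, or by how much. The figures above rest on assumed group sizes and assumed unconfirmed shares. No error rate can be given, because no null rate or decision rule is visible. This should be fixed before database lock, but it is a matter of clarifying a rule that the protocol already contains and does not invalidate the design.

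**What to change.** 1. In SAP 3.11.2 and protocol 11.1, define the numerator as a confirmed PR or CR, whichever the cohort requires. For patients in PR at screening only CR counts; the Group 1 formula does not reflect this, which is a separate point.
2. Take confirmation from the scan 6 weeks after the response-defining scan, with an allowance matching the protocol's 7-day imaging windows (42 ± 7 days, so 35 to 49 days). The protocol gives no window for the confirmatory scan itself, and a strict 42-day minimum could reject scans taken a few days early.
3. Class a conversion that is not confirmed, or has no confirmatory scan, as a non-response. Protocol 13.4.2 treats missing response data as non-response but does not say whether a missing confirmatory scan counts as missing.
4. Report the unconfirmed rate as a supportive line.
5. Restrict duration of response to confirmed responders, still dated from the first response-defining scan.
6. Reconcile the 4-week cells of Table 8 with its 6-week note, and state what applies in the PR rows.

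If unconfirmed responses are intended to count, say so in SAP 5.1.

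The cost is wording in the SAP and a clarification of the protocol. The scan is already scheduled. The downside is that the reported rate may be slightly lower.
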